#### 6.3.2.4 Other On-Treatment Procedures

- Dermatology referral and tissue collection/skin biopsy:

If a subject experiences a treatment-emergent rash of Grade  $\geq 2$ , consider referral to Dermatology for skin biopsy if clinically indicated per conventional (standard of care) rash management. See Section 5.4 for rash management.

*OPTIONAL: In the event that one or more standard of care skin biopsies are conducted, extra tissue may be collected for research (immune correlate assay to explore the mechanism of skin rash) only for patients who give optional consent for the extra tissue collection. Refer to the Lab Manual and Section 6.4.5 for additional information.*

#### 6.3.3 End-of-Treatment Study Procedures

- Clinical Assessments
  - Physical examination (including weight), may be done via a telemedicine visit
  - Vital Signs (BP and heart rate)
  - AE assessment
  - Performance status
- Laboratory Assessments
  - Hematology labs - CBC with differential and platelet count

- Blood chemistry assessment, including: ALP, ALT/AST, total bilirubin, calcium, BUN, creatinine, potassium, sodium, chloride, bicarbonate
- Thyroid function tests - including thyroid-stimulating hormone (TSH), reflex free T4, reflex total/free T3
- Serum PSA
- Whole blood peripheral immune markers
- Isolation of peripheral blood mononuclear cells (PBMC)
- Circulating tumor cells
- Circulating tumor DNA
- Tissue Collection/Biopsy (optional)
  - Tumor Tissue Collection: A CT-guided core biopsy is optional at End of Treatment. The same lesion that was biopsied during Screening should be biopsied whenever feasible.

#### **6.3.4 30-day Safety Follow Up (+/- 7 days)**

- Clinical Assessments
  - AE assessment (may be performed via telephone)
- Laboratory Assessments
  - Hematology labs - CBC with differential and platelet count
  - Blood chemistry assessment, including: ALP, ALT/AST, total bilirubin, calcium, BUN, creatinine, potassium, sodium, chloride, bicarbonate

#### **6.3.5 100-day Safety Follow-Up (+/- 14 days)**

- Clinical Assessments
  - AE assessment (may be performed via telephone; if AE assessment was done at EOT visit, 100-day Safety Follow-Up AE assessment not required)

#### **6.3.6 Long Term/Survival Follow-up**

Patients will be followed for overall survival every 90 days (+/- 30 days) from last dose of study treatment, until death, withdrawal of consent, or the end of the study, whichever occurs first.

Follow up will be conducted via chart review and/or telephone call.

End of study is defined as three years after last dose of study drug.

### **6.4 Correlative Studies**

#### **6.4.1 Metastatic Tumor Biopsy**

Metastatic tumor biopsies are only required if the patient has no previous metastatic biopsy (within 90 days of C1D1 without intervening systemic therapy).

Metastatic tumor biopsy at Screening is optional.

Assays to be performed include RNA-seq, targeted genomic sequencing, histological assessment, and tumor content permitting, additional IHC and/or DNA-seq.

Metastatic tumor biopsy is optional at PD.

#### **6.4.2 Peripheral blood immune profiling**

The [name] laboratory at UCSF will perform whole blood immune profiling for this study. Research blood (6 heparin green top tubes) will be collected C1D1 (pre-dose), C2D1, C3D1 (pre-dose), and EOT and transported to the [name] laboratory as per instructions in the Lab Manual.

#### **6.4.3 Circulating tumor cells**

Circulating tumor cells were analyzed using the Epic Sciences' platform. Morphology and heterogeneity, quantification of total number of CTCs, and expression of cell surface markers including AR, CD46, and CK, were analyzed. As of Protocol Amendment 1.8 dated 07-24-2023, Epic Sciences is no longer providing analysis of the samples. Blood will continue to be collected on C1D1, C2D1, C3D1, and EOT, and will be stored at the UCSF CTSI Lab. All samples stored at Epic Sciences will be returned to UCSF, and will be stored in the CTSI Lab.

#### **6.4.4 Circulating tumor DNA**

The [name] laboratory at UCSF will analyze circulating tumor DNA for genomic alterations including alterations of *RB1*, *TP53*, and *PTEN*. In addition, 5-hydroxy methyl cytosine (5-hmC) sequencing of ctDNA will be performed to infer gene expression of key genes of interest including AR, ASCL1, EZH2, RB1, PTEN, TP53, and CTNNB1. Plasma for ctDNA analyses will be collected on C1D1, C2D1, C3D1, and EOT.

#### **6.4.5 Immune correlate assay to explore the mechanism of skin rash**

If a subject experiences a treatment-emergent rash of Grade  $\geq 2$ , consider referral to Dermatology for skin biopsy if clinically indicated per conventional (standard of care) rash management. See Section 5.4 for rash management.

OPTIONAL: In the event that one or more standard of care skin biopsies are conducted, extra tissue may be collected for research (immune correlate assay to explore the mechanism of skin rash) only for patients who give optional consent for the extra tissue collection (Refer to the Lab Manual). The risk of obtaining additional skin biopsy specimens at the time of a standard of care skin biopsy procedure will be minimized. The biopsy site and number of punches/samples obtained will be determined in consultation with the professional performing the procedure based on safe accessibility and size of lesion.

### **6.5 Use of Concurrent/Concomitant Medications**

#### **6.5.1 Prohibited Concomitant Medications**

Participants are prohibited from receiving the following therapies during the Screening and Treatment Phase (including retreatment for post-complete response relapse) of this trial (see Appendix 4):

- Antineoplastic systemic chemotherapy or biological therapy other than LHRH analogue
- Immunotherapy not specified in this protocol
- Chemotherapy not specified in this protocol
- Investigational agents not specified in this protocol
- Radiation therapy
  - Note: Radiation therapy to a symptomatic solitary metastatic lesion or to the brain may be allowed at the investigator's discretion.

Live vaccines within 30 days prior to the first dose of study treatment and while participating in the study. Examples of live vaccines include, but are not limited to, the following: measles, mumps, rubella, varicella/zoster, yellow fever, rabies, BCG, and typhoid vaccine. Seasonal influenza vaccines for injection are generally killed virus vaccines and are allowed; however, intranasal influenza vaccines (e.g., FluMist®) are live attenuated vaccines and are not allowed.

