## Abstract

Title	A Phase 2 Study of Apalutamide Plus Cetrelimab in Patients with Treatment-Emergent Small Cell Neuroendocrine Prostate Cancer
Study Description	Phase 2 single arm, Simon two stage evaluation of the combination of apalutamide plus cetrelimab in patients with mCRPC and histologic and/or genomic evidence of treatment-emergent small cell neuroendocrine prostate cancer who have previously progressed on at least one prior androgen signaling inhibitor. The primary study endpoint is composite response rate as defined by PSA50 response and/or objective response by RECIST 1.1 criteria.
Phase of Study	Phase 2
Investigational Products	Apalutamide, Cetrelimab
Study population	Male, adult (18 years of age and older) patients with metastatic castration resistant prostate cancer (mCRPC) with disease progression (PD) on at least one second generation androgen signaling inhibitor, including abiraterone acetate, apalutamide, darolutamide, and/or enzalutamide and evidence of treatment-emergent small cell neuroendocrine cancer (t-SCNC). All races/ethnicity are included.
Primary Objective	To determine the composite response rate as defined by achieving one or more of the following at any time point during study treatment: 
 
• PSA50, decline from baseline in serum PSA of <math>\geq 50\%</math>, confirmed by repeat measurement <math>\geq 4</math> weeks later
 
• Objective response by RECIST 1.1 criteria
 

Secondary Objectives	
 
1. To determine safety of the combination as determined by CTCAE version 5.0
 
2. To determine the median radiographic progression-free survival by PCWG3 criteria
 
3. To determine the PSA50 and PSA90 response proportion achieved
 
4. To determine the median PSA progression-free survival
 
5. To determine the median overall survival
 
6. To determine the objective response rate and median duration of response by RECIST 1.1 criteria
 

Sample Size	N = 24 patients.

Duration of Study Treatment	Participants may continue study treatment from the time of treatment initiation until confirmed radiographic PD per PCWG3/RECIST 1.1 criteria, unequivocal clinical progression, unacceptable toxicity, or patient withdrawal, whichever occurs first – for a maximum of 24 months.

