## 2.2 Primary Objective and Endpoints

Primary Objective	Endpoints	Time Frame
To determine the composite response rate (achieving one or more of the endpoints) of apalutamide plus cetrelimab.	

PSA50 (decline from baseline in serum PSA of <math>\geq 50\%</math>, confirmed by repeat measurement <math>\geq 4</math> weeks later)* AND/OR

Objective response by RECIST 1.1 criteria**

	From initiation of study treatment until discontinuation of treatment (maximum of 2 years).

\* to be considered evaluable for PSA50 response, patients must have baseline PSA level  $> 2$  ng/mL

\*\* to be considered evaluable for objective response, patients must have measurable soft tissue disease by RECIST 1.1 criteria on baseline scan assessment

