### 7.1.2 Disease Parameters

#### Measurable disease

Measurable lesions are defined as those that can be accurately measured in at least one dimension (longest diameter to be recorded) as  $\geq 20$  mm ( $\geq 2$  cm) by chest x-ray or as  $\geq 10$  mm ( $\geq 1$  cm) with CT scan, MRI, or calipers by clinical exam. All tumor measurements must be recorded in millimeters (or decimal fractions of centimeters).

Note: Tumor lesions that are situated in a previously irradiated area considered measurable only if radiographic evidence of progression following completion of prior radiation treatment.

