## **Evaluation of Best Overall Response**

The best overall response is the best response recorded from the start of the treatment until disease progression/recurrence (taking as reference for progressive disease the smallest measurements recorded since the treatment started). The participant's best response assignment will depend on the achievement of both measurement and confirmation criteria.

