### **Definition of Progressive Disease**

A composite definition of PD will be defined by first occurrence of any one of the following:

- Appearance of new metastatic lesions outside the bone
- New metastatic lesions on bone scan confirmed as described above
- Development of an indication for radiotherapy while on treatment
- Unequivocal progression of non-target lesions
- Global deterioration of health status requiring discontinuation of treatment without objective evidence of PD
- Development of an indication for non-protocol systemic therapy

Patients experiencing radiographic progression in the absence of clinical progression are allowed to remain on treatment until follow up scan confirms progression.

Note that PSA progression (as defined above) alone does not meet the criteria for progressive disease.

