#### 8.3.2 Primary Analysis (or Analysis of Primary Endpoints)

The composite response rate is the primary endpoint of the study, defined as:

- $\geq 50\%$  decline from baseline PSA (defined by C1D1 value), confirmed by repeat measurement  $\geq 3$  weeks later AND/OR
- Objective tumor response by RECIST 1.1 criteria AND/OR

The composite response rate along with 95% confidence interval will be reported.

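### The PSA half of the primary endpoint has no cut-off at on-study radiotherapy, so a confirmed PSA fall first seen afterwards can be scored as a drug response

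*Combined protocol and SAP*

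**What the plan says.** **Radiotherapy.** Section 6.5.1, repeated in Appendix 4, prohibits radiotherapy during screening and treatment, then makes an exception: "Radiation therapy to a symptomatic solitary metastatic lesion or to the brain may be allowed at the investigator's discretion".

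**Primary endpoint.** The Abstract states the objective as "To determine the composite response rate as defined by achieving one or more of the following at any time point during study treatment". Section 2.2 gives the time frame as "From initiation of study treatment until discontinuation of treatment (maximum of 2 years"). Section 8.3.2 has two components: a fall of at least 50%, worded as "decline from baseline PSA (defined by C1D1 value), confirmed by repeat measurement", and "Objective tumor response by RECIST 1.1 criteria". None of these places mentions radiotherapy or progression as the end of the counting window. The PSA definitions in Section 7.1.4 do not either.

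**Progression and best response.** The composite definition of progression in Section 7.1.4 includes "Development of an indication for radiotherapy while on treatment". The same section says: "The best overall response is the best response recorded from the start of the treatment until disease progression/recurrence".

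**Irradiated lesions.** Section 7.1.2 deals with radiotherapy given before a lesion is chosen for measurement: "Tumor lesions that are situated in a previously irradiated area considered measurable only if radiographic evidence of progression following completion of prior radiation treatment". It does not address PSA.

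**Stopping treatment.** Section 3.5 lists radiographic progression, unequivocal clinical progression and receipt of therapy outside the protocol. It does not list an indication for radiotherapy, and does not say whether radiotherapy permitted under Section 6.5.1 is therapy outside the protocol. Patients whose only progression is by PSA stay on treatment.

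**The concern.** Radiotherapy to a metastasis can lower serum PSA without any contribution from the study drugs. A single-arm trial has no control group in which the same co-intervention would show up, so a PSA50 produced this way is credited to apalutamide plus cetrelimab. A patient whom Section 7.1.4 already classes as progressed could then be counted as a primary responder.

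The decision rests on few events: stop at 2 or fewer of 14, reject the null at 8 or more of 24. One miscounted patient can move the result at either step. With no rule fixed in advance, the status of such a patient would be argued after the data are known.

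**Working it through.** **1. Is the RECIST half open?** An on-treatment indication for radiotherapy is progression, and best overall response is recorded only until progression (both Section 7.1.4). Shrinkage first seen after on-treatment radiotherapy therefore falls outside the response window. Section 8.3.2 does not cross-refer to these rules, but they exist.

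**2. Is the PSA half open?** The best-response rule sits with the tumour response criteria, and nothing carries it over to PSA50. The Abstract and Section 2.2 run the window to the end of treatment. PSA is drawn on Day 1 of each cycle (Section 6.1), so later falls would be captured.

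**3. A constructed case** (invented values). PSA is 12 at C1D1, so the PSA50 threshold is 6.0. PSA is 13 at C2 and C3; a solitary lesion is irradiated in cycle 3; PSA is 5.5 at C5 and 5.0 at C6.
- Fall at C5: 1 − 5.5/12 = 54.2%.
- Fall at C6, scheduled 28 days later: 1 − 5.0/12 = 58.3%.

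This meets the 4-week confirmation in Section 2.2 and the 3-week confirmation in Section 8.3.2. If treatment has continued, the patient is a primary responder, although PSA had not fallen before radiotherapy.

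**4. The plan's own design** (Section 8.1.1: n1 = 14, stop at 2 or fewer; N = 24, reject at 8 or more). The exact rejection probability at true rate p is

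R(p) = Σ (x = 3 to 14) C(14,x) pˣ (1−p)^(14−x) × P[Bin(10,p) ≥ max(0, 8−x)].

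- R(0.40) = 0.8024, which reproduces the stated power of 80.2%.
- R(0.15) = 0.0194. The stated 0.025 therefore reads as the design limit, not the attained error.

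**5. Sensitivity of the rule.** If a share q of true non-responders is scored as responders, the counted rate under the null is p = 0.15 + 0.85q.

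| Counted rate p | q = (p − 0.15)/0.85 | R(p) |
|---|---|---|
| 0.15 | 0 | 0.019 |
| 0.16 | 0.01/0.85 = 1.2% | 0.028 |
| 0.18 | 0.03/0.85 = 3.5% | 0.052 |

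The documents give no value for q. Write it as the share irradiated times the share of irradiated non-responders who then reach PSA50; both are assumptions.
- 5% × 10%: q = 0.5%, p = 0.154, R = 0.023, still below 0.025.
- 10% × 25%: q = 2.5%, p = 0.171, R = 0.040.

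**6. Without any assumed rate.** One miscounted patient turns 7/24 (29.2%, do not reject) into 8/24 (33.3%, reject), or 2/14 (stop) into 3/14 (continue).

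**7. Price of a cut-off.** If the rule also removes a share f of true responders (assumed), the alternative becomes 0.40 × (1 − f).

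| f | Counted rate | Power |
|---|---|---|
| 0 | 0.40 | 0.802 |
| 2.5% | 0.39 | 0.774 |
| 5% | 0.38 | 0.743 |
| 10% | 0.36 | 0.674 |

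**The case against.** **The route is narrow.** Radiotherapy is generally prohibited; the exception covers one symptomatic solitary lesion or the brain. A false PSA50 needs the irradiated site to supply most of the serum PSA, a confirmed fall of at least half from C1D1, and continued dosing. Section 1.2 describes low PSA relative to disease burden as a feature that enriches for this tumour type. All of this stands and limits how often the case could arise.

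**Treatment may end anyway.** A lesion symptomatic enough to irradiate might be judged unequivocal clinical progression, or the radiotherapy might be taken as therapy outside the protocol. Either would end treatment under Section 3.5 and close the window in Section 2.2. This stands as a possible reading, but Section 3.5 does not say so, and radiotherapy that Section 6.5.1 expressly allows does not obviously fall under that item. The text is ambiguous; it cannot be said that nothing could close the PSA window.

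**Any misclassified patient turns 7 into 8.** True. The step shows how sensitive the rule is, not how likely this error is.

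**A stronger reading.** A reader might infer that tumour shrinkage after radiotherapy is also scored as a drug response. The two rules in Section 7.1.4 do not support that for on-treatment radiotherapy.

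**Conclusion.** The point holds for the PSA50 component only, and as something that can happen, not something that will. Permitted radiotherapy, an endpoint window running to the end of treatment, and the absence of a PSA cut-off together allow a confirmed PSA fall first seen after radiotherapy to count as a primary response whenever study treatment continues. Whether it continues is left unclear by Sections 3.5, 6.5.1 and 7.1.4.

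The size cannot be estimated from the documents. A reader might take the figures above as a forecast of type I error; they are not. They show that about one extra percentage point on the 15% null takes the exact rejection probability from 0.019 past the stated 0.025, to 0.028. A smaller inflation would stay within it. The 7/24 to 8/24 step needs no assumed rate.

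This is a cheap improvement to the analysis wording, not a flaw in the design.

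**What to change.** **In Section 8.3.2:**
- Apply the plan's own progression cut-off to PSA: a PSA50 or PSA90 first met after the first on-study radiotherapy does not count towards composite response, PSA50 or PSA90.
- A patient who met the criterion before radiotherapy remains a responder. Any other irradiated patient stays in the denominator as a non-responder.
- State by cross-reference that the best-response and progression rules of Section 7.1.4 govern the RECIST component.
- Report the number of patients irradiated, and the composite rate without this rule as a sensitivity analysis.

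**Elsewhere:** record the dates of on-study radiotherapy. Reconcile Sections 3.5, 6.5.1 (with Appendix 4) and 7.1.4 on the status of permitted radiotherapy. This review takes no view on whether radiotherapy should be allowed or whether treatment should stop after it.

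**Cost:** analysis wording and one recorded date; N and the cut-offs do not change. The downside is that a true late drug response in an irradiated patient is lost. If that removed 2.5% to 10% of true responders (assumed), power at 40% would fall from 0.802 to between 0.774 and 0.674. The sensitivity analysis would show how many responses the rule removed.

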**COVID-19 vaccine is allowed.**

**Medications or vaccinations** specifically prohibited in the exclusion criteria are not allowed during the ongoing study. If there is a clinical indication for any medication or vaccination specifically prohibited during the study, discontinuation from study therapy or vaccination may be required. The final decision on any supportive therapy or vaccination rests with the investigator and/or the participant's primary physician. However, the decision to continue the participant on study treatment requires the mutual agreement of the Principal Investigator and subject.

### Prohibited Therapies

- Aminophylline/theophylline
- Atypical antipsychotics (e.g., clozapine, olanzapine, risperidone, ziprasidone)
- Bupropion
- Lithium
- Meperidine and pethidine
- Phenothiazine antipsychotics (e.g., chlorpromazine, mesoridazine, thioridazine)
- Tricyclic and tetracyclic antidepressants (e.g., amitriptyline, desipramine, doxepin, imipramine, maprotiline, mirtazapine)
- Systemic immunotherapy or immunosuppressants (e.g., ipilimumab, cyclosporine, infliximab). However, the use of immunosuppressive medications for the management of irAEs, IRRs, or in subjects with contrast allergies is acceptable.
- Live or live attenuated vaccines; annual inactivated influenza vaccine is permitted
- Other anticancer therapies, excluding GnRH analog

### 6.5.2 Acceptable Concomitant Medications/Supportive Care

Participants should receive appropriate supportive care measures as deemed necessary by the treating investigator. Suggested supportive care measures for the management of AEs with potential immunologic etiology are outlined along with the dose modification guidelines. Where appropriate, these guidelines include the use of oral or IV treatment with corticosteroids, as well as additional anti-inflammatory agents if symptoms do not improve with administration of corticosteroids. Note that several courses of steroid tapering may be necessary as symptoms may worsen when the steroid dose is decreased. For each disorder, attempts should be made to rule out other causes such as metastatic disease or bacterial or viral infection, which might require additional supportive care. The treatment guidelines are intended to be applied when the Investigator determines the events to be related to cetrelimab.

Note: If after the evaluation of the event, it is determined not to be related to cetrelimab, the Investigator does not need to follow the treatment guidance. Refer to guidelines regarding dose modification and supportive care.

Patients are recommended to use bone-modifying agents (e.g. denosumab, zoledronic acid) during Screening and Treatment phases of the study to decrease risk of fracture.

LHRH analogues are required during Study Treatment except for patients with history of bilateral orchiectomy.

Patients are recommended to taper off prednisone prior to study enrollment but are allowed to take doses up to  $\leq$  10 mg daily prednisone or prednisone equivalent. Doses of steroids higher than prednisone 10 mg daily (or prednisone equivalent) are permitted only for the treatment of immune related AEs.

Treatment with antiemetic therapy will be permitted, if clinically indicated.

Treatment with filgrastim or other colony stimulating factors will be permitted for Grade 3 or higher hematologic toxicity as per Package Insert but may not be used prophylactically.

Treatment required for care of complications/AEs arising from the cancer and/or treatment will be permitted.

